### 7.3.2 Vital Signs (blood pressure)

SBP and DBP will be evaluated at the timepoints specified in [Table 1](#).

All measurements will be made in duplicate within a 5-min interval. Subjects should be resting in a quiet, supervised setting with minimal stimulation (e.g. no television, loud music, computer games) and lay in a supine position for 5 min (whenever possible) before each measurement. Blood pressure measurements must be performed before the lung function assessments and the blood tests, as specified in [Table 1](#).

Acceptable time deviations from theoretical post-dose timepoints are  $\pm 10$  min.

### 7.3.3 Electrocardiogram Assessments

ECG assessments will be performed at the timepoints specified in [Table 1](#).

Subjects should be resting in a quiet supervised setting with minimal stimulation (e.g. no television, loud music, computer games). ECG recordings will be performed either before or after blood pressure measurements, and must be performed before the lung function assessments and the blood tests, as specified in [Table 1](#).

At screening, a triplicate 12-lead digitised ECG recording will be performed. The values of all ECG parameters and the overall ECG evaluation will be reported in the eCRF. The average of the triplicate recordings will be used to assess the subjects' eligibility (see Exclusion criterion #12 in [Section 4.3](#)). In case abnormal CS ECG results are obtained at screening, the subject will be asked to return to the investigational site once before randomisation to repeat the ECG measurement. If, at that time, ECG interpretation is not considered abnormal clinically significant, the subject can be included in the study. Otherwise, the subject will be discharged and recorded as a screening failure.

During the Investigational Phase (TP1 and TP2) and the Early Termination visit, single ECGs will be performed for safety assessments. Acceptable time deviations from theoretical post-dose timepoints are  $\pm 10$  min.

### 7.3.4 Blood Sample Collection

Blood samples will be collected at screening, as specified in [Table 1](#).

|  |                      |
|--|----------------------|
| Clinical Study Code No.: CLI-05993AB6-07 | Version No.: 2.0     |
| EUDRACT No.: 2022-000536-36              | Date: 30 August 2022 |

Laboratory tests can be repeated, if deemed necessary by the Investigator, to assess the subject's safety or to confirm his/her eligibility.

Approximately 20 mL of blood will be collected according to the local procedures, to assess the following parameters:

- Routine blood haematology: red blood cells (RBC) count, white blood cells (WBC) count and differential count (absolute value and %), total haemoglobin (Hb), haematocrit (Hct), platelets (PLT) count;
- Serum clinical chemistry: creatinine, urea, phosphate, aspartate aminotransferase (AST), alanine aminotransferase (ALT), gamma-glutamyl transpeptidase ( $\gamma$ -GT), total bilirubin, alkaline phosphatase, total cholesterol, triglycerides, sodium (Na), potassium (K), calcium (Ca), chloride electrolytes (Cl);
- Serum pregnancy test (in case of WOCBP) and FSH test (in case of post-menopausal women, if the FSH value is deemed necessary by the investigator).

In case clinically significant abnormal laboratory values are obtained at screening that could indicate a temporary condition (see Exclusion criteria #13, #14 and #15 in [Section 4.3](#) for details), the subject will be asked to return to the centre once before randomisation, to repeat the test. If, at that time, no clinically significative abnormalities are observed, the subject can be included in the study. Otherwise, the subject will be discharged and recorded as a screening failure.

Blood collection and sample preparation will be performed according to the procedures provided by the local laboratory, which will be in charge of transmitting the results to the Investigator for evaluation. Only CS abnormal values of laboratory results will be entered in the eCRF by the Investigator, and AEs/serious adverse events (SAEs) will be reported. The normal ranges will be provided by the local laboratory and included in the eCRF

### 7.3.5 Urine Sample Collection

A urine sample will be collected from all subjects at screening for the urinalysis (quantitative [proteins] and qualitative [ketones, microscopic examination of the sediment]).

During the investigational phase (TP1 and TP2) and the Early Termination visit (if relevant), urine will be collected from childbearing potential female subjects for laboratory pregnancy tests.

### 7.3.6 Administered Questionnaires

#### 7.3.6.1 Asthma Control Questionnaire

The five-item ACQ-5 questionnaire will be used for the evaluation of each subject's asthma control level [\[19\]](#). The questionnaire will be administered at pre-screening or screening to assess eligibility, and at TP1 (before randomisation) to confirm eligibility.

The ACQ-5 is a self-administered questionnaire which includes five questions on asthma symptoms experienced during the past week. Subjects must score each of the questions on a scale of 0 to 6, where 0 represents excellent control of the symptom and 6 represents extremely poor control. The overall score of the ACQ-5 is the mean of the five responses [\[19\]](#).

Subjects must have an overall score of <1.5 to be eligible for inclusion in this study (see Inclusion criterion #7, [Section 4.2](#)).

|  |                      |
|--|----------------------|
| Clinical Study Code No.: CLI-05993AB6-07 | Version No.: 2.0     |
| EUDRACT No.: 2022-000536-36              | Date: 30 August 2022 |

## 8. EFFICACY ASSESSMENTS

No efficacy assessments are planned in this study.

## 9. SAFETY ASSESSMENTS

The **primary objective** of this study is to compare the potential for bronchoconstriction [REDACTED] of the HFA-152a propellant *versus* [REDACTED] the HFA-134a propellant when administered alone (not in combination with other active compounds).

The potential for bronchoconstriction will be assessed through centralised spirometry assessments performed at TP1 and TP2, as described in [Section 7.3.1](#). At each treatment period, FEV1 and PEF will be assessed in pre-dose: 45 min and 15 min before T0; and in post-dose: 5 min, 15 min, 30 min, 1 h, 1 h 30 min and 3 h after T1.

The following safety variable will be considered for the evaluation of the potential for bronchoconstriction of each propellant:

- Relative change from baseline\* in FEV1 at the 15 min post-dose timepoint.

In addition, the following safety variables will be considered to complete the evaluation of the potential for bronchoconstriction of each propellant:

- Relative change from baseline\* in FEV1 at all the other post-dose timepoints (5 min and 30 min, 1 h, 1 h 30 min and 3 h after T1);
- Absolute change from baseline\* in FEV1 at all post-dose timepoints (5 min, 15 min, 30 min, 1 h, 1 h 30 min and 3 h after T1);
- Number and percentage of subjects with a relative change from baseline\* in FEV1 at each post-dose timepoint <-15%;
- Number and percentage of subjects with a relative change from baseline\* in FEV1 at any post-dose timepoint <-15%;
- Change from baseline\* in FEV1 area under the concentration-time curve from time zero to 3 hours (AUC0-3h);
- Relative change from baseline\* in PEF at all post-dose timepoints;
- Absolute change from baseline\* in PEF at all post-dose timepoints;
- Number and percentage of subjects with use of rescue medication in the 3 h after T1;
- Mean use (puffs) of rescue medication in the 3 h after T1.

\* The baseline FEV1 and PEF values are the mean of the 2 pre-dose assessments (i.e. performed 45 min and 15 min before T0).

|  |                      |
|--|----------------------|
| Clinical Study Code No.: CLI-05993AB6-07 | Version No.: 2.0     |
| EUDRACT No.: 2022-000536-36              | Date: 30 August 2022 |

The **secondary objective** of the study is to evaluate the general safety and tolerability of the two propellants.

The general safety of the propellants will be assessed at TP1 and TP2, throughout local safety ECGs (as described in [Section 7.3.3](#)), vital signs (as described in [Section 7.3.2](#)), and recording of AEs and concomitant medications.

The following safety variables will be considered for the evaluation of the general safety and tolerability of each propellant:

- AEs and AEs of particular interest (bronchospasm, cough, dysphonia, hoarseness);
- Vital signs (SBP and DBP);
- 12-lead ECG parameters: HR, QTcF, PR and QRS.

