At each timepoint specified in [Table 1](#), subjects will perform three attempts for the measurement of FEV1 and peak expiratory flow (PEF). In order to be considered as technically satisfactory attempts, measurements should be free from cough and false-start. The highest value (in L) of FEV1 and PEF from three technically satisfactory attempts (not necessarily coming from the same curve) will be recorded. The two largest FEV1 measurements must be within 150 mL of each other (or 100 mL, if the forced vital capacity [FVC] value is  $\leq 1$  L). If the difference is larger, additional spirometry assessments (up to 8) will be made until the above criterion is met. If, at the end, the tests are not within 150 mL, the highest value of FEV1 and PEF will be recorded and used for eligibility or continuation criteria.

In case lung function measurements obtained at screening were below the expected value, (see Inclusion criterion #4 in [Section 4.2](#)), the subject will be asked to return to the investigational site once before randomisation to repeat the test. If, at that time, FEV1  $\geq 60\%$  of the predicted normal value and  $\geq 1.5$  L, the subject can be included in the study. Otherwise, the subject will be discharged and recorded as a screening failure.

If a subject shows a progressive reduction in FEV1 with each subsequent blow, with cumulative drop above 15% of the starting value, the test procedure may be terminated in the interest of the subject's safety. During the 3 h post-dose serial spirometry, the use of rescue medication should

|  |                      |
|--|----------------------|
| Clinical Study Code No.: CLI-05993AB6-07 | Version No.: 2.0     |
| EUDRACT No.: 2022-000536-36              | Date: 30 August 2022 |

be as limited as possible and rescue medication intake must be under medical control. The serial spirometries can be discontinued after the intake of rescue medication, based on the Investigator's judgement. In this case and if deemed necessary, a safety spirometry can be performed by the site. Details on intake of rescue medication during the treatment periods will be recorded in the eCRF.

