- If the date(time) is missing or incomplete for a specific post-dose time point, then it will be imputed as the date(time) of the previous time point + the theoretical time interval between the two time points.
- If 2 or more consecutive post-dose time points have a missing or incomplete date(time), then the AUC will also be set to missing.

For FEV₁, the following abnormality categories are defined:

- Relative changes from baseline:
 - Decrease from Baseline >15 %

Potential exclusion of lung function parameters based on time window not respected will be discussed during the review of the data by the Chiesi team. Decisions on whether values are to be excluded from the analysis will be fully documented in the DRR.

2.5.3 *Inferential statistics*

Primary objective (i.e. evaluation of the potential for bronchoconstriction of each propellant):

- The relative change from baseline in FEV₁ at the 15 min post-dose time point will be analysed using an analysis of covariance (ANCOVA) model, including treatment group, subject and period as fixed effects, and FEV₁ baseline (mean of the two measurements at 45 min and 15 min pre-dose in each treatment period) as a covariate.

The adjusted mean relative change from baseline obtained with each treatment and the adjusted mean difference between HFA-152a and HFA-134a with their 95% CIs and p-values will be estimated by the model.

	Statistical Analysis Plan	
CLI-05993AB6-07		Final 1.0 of 22DEC2022

Other variables completing the evaluation of the potential for bronchoconstriction of each propellant:

- The relative changes from baseline in FEV₁ at all the other post-dose time points (5 min, 30 min, 1 h, 1 h 30 min and 3 h) will be analysed using the same model used for the relative change from baseline in FEV₁ at 15 min post-dose;
- The absolute changes from baseline in FEV₁ at all post-dose time points (5 min, 15 min, 30 min, 1 h, 1 h 30 min and 3 h) will be analysed using the same model used for the relative change from baseline in FEV₁ at 15 min post-dose.

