2.5.4 Presentation of results

Lung function parameters will be summarised by means of descriptive statistics at each analysis time point by treatment. Actual values, absolute and relative changes from baseline (FEV₁ and PEF only) will be tabulated.

For the ANCOVA models, adjusted mean in each treatment and the adjusted mean difference between HFA-152a and HFA-134a, their 95% CIs and related p-values will be provided and tabulated from the ANCOVA. This tables will also include the type III p-values associated to model effects.

The number and percentage of subjects with FEV₁ abnormal relative changes from baseline will be presented at each post-dose time point and at the worst-case analysis visit by treatment.

The change from baseline in FEV₁ AUC_{0-3h} will be summarised by means of descriptive statistics by treatment.

All lung function parameters will be listed.

Graphs of the mean changes (both absolute and relative) from baseline over time will be prepared for FEV₁ and PEF by treatment.

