5.3 IMPUTATION AND ROUNDING RULES

5.3.1 *Missing values*

[figure not shown]
No imputation of missing values will be done (i.e. observed cases analysis).

5.3.2 *Handling partially or completely missing dates in calculations*

In case of missing date(time)s for FEV₁ assessments, needed for the calculation of AUC_{0-3h}, these cases will be discussed and documented in the DRR.

Partially missing date of first diagnosis event will be imputed as follows for the calculation of time since event:

- Missing day will be imputed with the first day of the month
- Missing day and month will be imputed with 1st JAN

	Statistical Analysis Plan	
CLI-05993AB6-07		Final 1.0 of 22DEC2022

Partially missing date of most recent exacerbation event will be imputed as follows for the calculation of time since event:

- Missing day will be imputed with the last day of the given month
- Missing day and month will be imputed with 31st DEC

5.3.3 *Values below or above a threshold*

Safety values expressed as below (or above) the limit of quantification will be imputed by the value of the quantification limit itself. Listings will always show the non-imputed values.

5.3.4 *Rounding of derived variables*

Derived variables will be rounded at display level:

- AE duration will be presented with 1 decimal.
- Mean of duplicates (blood pressure)/triplicates (ECG) will be rounded to the nearest integer.
Note: since the rounding is applied at display level, in the listings, the change from baseline could be slightly different to the listed value at time point t – baseline value
- Mean of duplicates (lung function) will be rounded to same number of decimal places as the individual values.
Note: since the rounding is applied at display level, in the listings, the change from baseline could be slightly different to the listed value at time point t – baseline value
- FEV₁ AUC_{0-3h} will be rounded to the same number of decimal places as the actual FEV₁ values.
- Relative change from baseline will be presented with 1 decimal.
- Time since first diagnosis and most recent exacerbation will be presented with 1 decimal.

5.3.5 *Outliers*

Potential outliers will be discussed during the review of the data by the Chiesi team. Decisions on whether values are to be excluded from the analysis will be fully documented in the DRR.

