5.4 PRESENTATION OF RESULTS

5.4.1 *Calculation of descriptive statistics and percentages*

For continuous parameters, full descriptive statistics will only be presented if there are at least 2 non-missing observations. Alternatively, only the number of non-missing data points and mean are shown.

Descriptive statistics will include the number of non-missing data points, the arithmetic mean, the standard deviation (SD), the median, minimum and maximum.

Descriptive statistics of safety parameters will additionally include 95% (or 90%) confidence interval (CI) on the mean (based on t-distribution, without continuity correction).

Statistical Analysis Plan

CLI-05993AB6-07

Final 1.0 of 22DEC2022

Mean, median, SD and CI will be presented with one more decimal place than the individual values. Minimum and maximum will be presented with the same number of decimal places than the individual values.

For event-type data, the denominator will be all subjects in the analysis set and phase and period. All treatments will be shown, even if no events are present.

P-values will be presented with three decimal places (Note: any p-value less than 0.001 will be presented as <0.001 and any p-value greater than 0.999 will be presented as >0.999) and test statistics with two decimal places.

For frequency tabulations, missing values will not be included in the denominator count when computing percentages.

Percentages will be shown with one decimal place.

5.4.2 *Presentation of treatments*

The following treatment labels will be used in the tables, listings and figures:

When presented by treatment:

- HFA-152a
- HFA-134a

When presented by treatment sequence:

- HFA-152a-HFA-134a
- HFA-134a-HFA-152a

Unless specified otherwise, an overall column, to summarise all subjects over treatments, will be presented only in tables showing data that are not affected by the study treatment, as well as in the AEs summaries. The overall column will be shown last.

5.4.3 *Ordering in tables, listings and figures*

If the treatments are presented as columns, tables will be sorted by analysis visit and time point. Otherwise, tables will be sorted first by treatment, then by analysis visit and time point.

The test treatment will be shown first, and then reference treatment: HFA-152a, HFA-134a.

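### The counts of subjects with an FEV1 fall beyond -15% ignore rescue, so early rescue lowers them and narrows any difference between propellants

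*Protocol*

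**What the plan says.** - **The event.** Protocol 9 (repeated in 12.3.6) lists two counts among the variables that complete the bronchoconstriction evaluation: subjects with a relative FEV1 change "at each post-dose timepoint <-15"%, and the same "at any post-dose timepoint <-15"%. SAP 2.5.2 defines the abnormality as "Decrease from Baseline >15"%. It is a spirometry value only, and rescue plays no part in it.
- **The output.** SAP 2.5.4 says that subjects with "abnormal relative changes from baseline will be presented at each post-dose time point and at the worst-case analysis visit by treatment" (Table 14.3.7.6). SAP 5.2.5 derives the worst case from all post-dose readings in the period, scheduled and unscheduled, with no cut at rescue.
- **Rescue.** Protocol 7.3.1 allows rescue in the 3 h after dosing; it is to be kept to a minimum and "rescue medication intake must be under medical control". The same section adds: "The serial spirometries can be discontinued after the intake of rescue medication, based on the Investigator's judgement". A safety spirometry by the site is then optional.
- **Missing readings.** SAP 5.3.1: "No imputation of missing values will be done (i.e. observed cases analysis"). SAP 5.4.1: "For frequency tabulations, missing values will not be included in the denominator count when computing percentages".
- **Rescue reporting.** SAP 2.6 and Table 14.3.8.1 give the subjects using rescue in the first 3 h, and the puffs, by treatment.

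Neither document says whether FEV1 readings after rescue are used, set aside or treated as an event.

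**The concern.** Protocol 1.2 explains that the trial exists because earlier studies gave the new propellant together with bronchodilators, so a bronchoconstrictor effect could have gone unseen. Taking post-rescue readings at face value brings back some of that masking within these rows. A subject treated because the airways were narrowing can appear as one whose FEV1 never fell beyond -15%. The more early rescue a propellant prompts, the more of its events are removed. What is at stake is the reading of the only subject-level count in the plan that is based on FEV1: a low count, or similar counts on the two propellants, could look more reassuring than it is.

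**Working it through.** **1. The plan's own figures.** The documents give no expected rate for the -15% rows and no rescue rate. Their only power statement (20 evaluable subjects, within-subject SD 8%, limits ±10%, 95% power) concerns the primary variable. By normal approximation SE = 8 × √(2/20) = 2.53 and power = 2Φ(10/2.53 − 1.96) − 1 = 95.4%. It has no bearing on these rows.

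**2. One subject traced through the rules.** Suppose the change is -12% at 5 min and rescue follows.
- *Series stopped:* the subject leaves the numerator and denominator of the later rows. The worst case is -12%, so the any-time-point row records a non-event.
- *Series continued:* later rows hold bronchodilated readings scored as not abnormal. The any-time-point row again records a non-event.
- *No post-dose reading at all:* the subject also leaves the any-time-point row.
- A fall beyond -15% recorded before rescue, or by an optional safety spirometry, still counts.

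**3. Direction.** If airway responses are held fixed and rescue does not deepen a fall, rescue can remove recorded events but cannot add them. This holds for the counts. A per-time-point percentage can move slightly the other way if a rescued subject who would not have been beyond -15% at that time leaves the denominator.

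**4. Count arithmetic (assumed: 24 treated, 6 would fall beyond -15% without rescue, r of them rescued before capture).**

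| r | Any-time-point row, subjects kept | If they leave the row | Fall or rescue |
|---|---|---|---|
| 0 | 6/24 = 25.0% | 6/24 = 25.0% | 6/24 = 25.0% |
| 2 | 4/24 = 16.7% | 4/22 = 18.2% | 6/24 = 25.0% |
| 4 | 2/24 = 8.3% | 2/20 = 10.0% | 6/24 = 25.0% |
| 6 | 0/24 = 0% | 0/18 = 0% | 6/24 = 25.0% |

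**5. With measurement noise (all inputs assumed).** A quarter of subjects react, with mean changes of -11, -20, -17, -10, -6 and -2% at the six times; the others have mean 0; the SD is 5 points. Rescue follows the 5 min reading and the series then stops.
- Reactor, not rescued: the chances of a reading beyond -15% are 0.212, 0.841, 0.655, 0.159, 0.036 and 0.005, so P(any) = 1 − (0.788 × 0.159 × 0.345 × 0.841 × 0.964 × 0.995) = 0.965.
- Reactor, rescued: only the 5 min reading counts, 0.212.
- Non-reactor: 1 − (1 − 0.00135)^6 = 0.008.

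Any-time-point row as planned:
- none rescued: 0.25 × 0.965 + 0.75 × 0.008 = 24.7%
- half of the reactors rescued: 0.125 × 0.965 + 0.125 × 0.212 + 0.006 = 15.3%
- all reactors rescued: 0.25 × 0.212 + 0.006 = 5.9%

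With rescue counted as an event, the figures are 24.7%, 25.2% (0.125 × 0.965 + 0.125 + 0.006) and 25.6% (0.25 + 0.006).

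**6. Between propellants (simulation, all inputs assumed).** 24 subjects and 600 trials per setting; maximal fall normal with SD 8, floored at 0, reached between 5 and 30 min; reading SD 3; rescue as soon as the underlying fall passes a threshold; readings after rescue average +3%; half of those rescued stop spirometry. Expected number of subjects in the any-time-point row for a mild propellant (mean maximal fall 4%) and a worse one (16%):

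| Rescue at a fall of | Observed, mild | Observed, worse | Difference | Fall or rescue, difference |
|---|---|---|---|---|
| never | 2.51 | 13.73 | 11.22 | 11.22 |
| 20% | 2.36 | 10.14 | 7.78 | 13.77 − 2.59 = 11.18 |
| 15% | 1.32 | 3.93 | 2.61 | 14.68 − 2.91 = 11.77 |
| 12% | 0.43 | 1.21 | 0.78 | 16.88 − 3.88 = 13.00 |

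The worse propellant always shows the higher count, but the difference shrinks from about 11 subjects to 8, 3 and 1.

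**7. Can other planned tables supply the missing number?** Table 14.3.7.6 gives subjects with a fall and Table 14.3.8.1 gives subjects with rescue. Some subjects will be in both, so the two counts cannot be added to give the number with either.

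**The case against.** The strongest reply is that the plan already shows what these rows miss. Protocol 9 lists rescue use in the same supportive set, and bronchospasm is an adverse event of particular interest with its own term search and subject counts by treatment (SAP 2.1.2, Table 14.3.1.10). A reader might infer that the -15% rows are the plan's only subject-level measure of bronchoconstriction, or that the signal disappears. The documents do not support either. In the example of step 5 with every reactor rescued, against a reference with no reactors, the any-time-point row would still read 5.9% against 0.8%, beside rescue use of 25% against 0%.

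A reader might also infer that the observed count must fall for the propellant that causes more rescue. That holds only with airway responses held fixed. A propellant that prompts more rescue because it constricts more may still show a higher count, as in step 6; the effect there is attenuation.

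There are partial safeguards. Unscheduled readings enter the worst case (SAP 5.2.5), and data review may consider other critical missing data (Protocol 12.3.2). The first depends on an optional reading being taken, and the second does not make rescue count. SAP 5.4.1 also has an all-subjects denominator for event-type data. If that applied here, a subject with no reading would stay in the row as a non-event, and the numerator would be no better.

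It stands that the rows are descriptive, that no decision rule uses them, and that rescue may be rare.

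**Conclusion.** The point holds in a limited form. Followed as written, the plan scores a subject rescued before a captured fall beyond -15% as a non-event in the any-time-point row. In later rows it either drops that subject or uses a bronchodilated reading. For given airway responses this can only lower the counts, and it attenuates the contrast between propellants when one prompts more early rescue.

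The direction follows from the rules themselves, given that rescue does not worsen FEV1. The size does not: every rate, depth of fall and rescue threshold used above is an assumption. With 24 subjects, each reclassified subject moves the percentage by 1/24 = 4.2 points. The primary ANCOVA at 15 min is a separate question and is not judged here. Because rescue and bronchospasm are reported by treatment, this is a cheap improvement to a supportive table and does not put the trial's conclusion in doubt.

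**What to change.** Change the SAP only (2.5.2, 2.5.4 and Table 14.3.7.6), before unblinding:

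- Add one any-time-point row: subjects with a relative FEV1 change below -15% at any post-dose time point, or with rescue use within 3 h after T1. The denominator is all subjects treated in that period.
- Keep the existing observed-reading rows, and flag readings taken after rescue in the lung function listing (16.2.8.4).
- Do not build the same composite for each time point. A rescue at 6 min would then count as an event at 3 h, while an unrescued subject who fell to -25% at 15 min and recovered would not. That mixes cumulative rescue with FEV1 at a single moment.
- Record the addition in SAP 6.1.

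The cost is a SAP revision, one table row and one listing flag; rescue times and puffs are already collected (SAP 2.6.1). A small downside is that rescue given for another reason would also count, but the rescue and lung function listings let a reader see such cases. The clinical rules on rescue need no change.
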